3.6 LABORATORY PROCEDURES

SPECIMEN COLLECTION, PREPARATION, HANDLING AND SHIPPING

Maximal infection control precautions will be implemented by research staff during all study visits and specimen collection procedures. These precautions include the use of gloves, safe venepuncture equipment, and a fit-tested N95 respirator during sputum collection. Sputum will be collected in well-ventilated areas, at an adequate distance from research staff and bystanders, to minimize infection risk.

All specimens will be collected in designated containers and labelled with printed, bar-coded labels containing the participant identification number, study visit, specimen type, intended assays, and specimen destination. Specimens designated for processing at the central laboratory will be stored at the appropriate temperature and transported under controlled conditions. At the central laboratory, samples will be aliquoted for testing or storage. All specimen preparation and handling will be conducted in BSL-2 or BSL-3 facilities (as approved by the AHRI/RC3ID Biosafety Committee), which are equipped for the safe handling of specimens potentially containing Mtb or HIV.

A specimen tracking log will be maintained to document all transfers between sites, including confirmation of appropriate temperature maintenance during transport. In instances where specialized laboratory assays required for the scientific aims of the project are not available in the central study

laboratory, samples may be exported to collaborating laboratories within South Africa or internationally. These transfers will be reviewed and approved by AHRI and the UKZN Biomedical Research Ethics Committee (BREC). Appropriate Material Transfer Agreements (MTAs) will be executed between collaborating institutions, and all necessary export permits will be obtained prior to shipment.

Non-human bacterial specimens may be stored indefinitely for future analyses, while human biological material may be stored for up to 20 years. Participants will be asked to provide broad informed consent for storage and future use of their biological samples including potential genetic testing, with all relevant information regarding genetic testing, storage duration, and governance included in the consent process.

LABORATORY EVALUATIONS/ ASSAYS

All laboratory procedures will be performed in accordance with approved biosafety and quality control standards and the relevant Standard Operating Procedures (SOPs). Samples will be processed at accredited study or reference laboratories using validated methods.

- (1) **Sputum.** Sputum samples (minimum 3mL) will be processed for Xpert (**GeneXpert Ultra**) or other similar assay, and for MGIT culture. Processing includes sample decontamination, aliquoting of specimens, testing of positive MGIT cultures to confirm Mtb status, and genetic sequencing of Mtb strains. Residual aliquots of sputum, MGIT culture, Mtb strains or extracted Mtb DNA may be stored.
- (2) **Venous blood.** 4-10mL of venous blood will be collected from child household contacts and 40mL of venous blood will be collected from participants in the case-control phenotyping and longitudinal TB-U sub-studies.
 - a. Whole blood will be instilled in **QuantiFERON Gold** assay tubes, incubated according to manufacturer instructions, and plasma analysed for interferon-gamma (IFN- γ) concentration. Supernatants may be stored.
 - b. Whole blood will be incubated with ESAT-6/CFP-10 peptide pools and appropriate controls. Following incubation, cells will be fixed, permeabilised, stored, and later assessed by flow cytometry using the **TB-TASA assay or other similar T-cell activation assay**.
 - c. Whole blood will also be processed for extraction and quantification of **cell-free Mtb DNA** using validated methods, or other similar assays for the detection of Mtb products.
 - d. **Clinical testing** will be performed at an accredited clinical lab and will include HIV testing and reflex viral load, HbA1c and full blood count.
 - e. Whole blood will be processed for biobanking and will include peripheral blood mononuclear cells (PBMCs), plasma, PaxGene tubes for RNA preservation, and buffy coats. DNA, RNA or other components may be extracted and stored. To address study objectives, stored biosamples may be used for assays to characterize cellular components and function, proteomics, lipidomics, transcriptomics, metabolomics, genomics, T cell receptor analysis, serologies and pharmacologic analyses. These

samples will be stored for future studies of TB disease and genetic studies under approved biobanking procedures.

- (3) Tongue swabs will be processed for detection of Mtb DNA by **PCR (e.g., PlusLife or other similar platform)**. A subset of swabs or eluted DNA may be frozen and stored for biobanking.
- (4) Facemask bioaerosol samples will be analysed for Mtb DNA using validated extraction and **PCR protocols** or other similar assay.
- (5) Exhaled breath condensate (EBC)samples will be collected in sterile tubes and condensed in an ice-filled cooling chamber mounted around the sterile tube within the device and shipped to the Desmond Tutu Health Foundation (DTHF) or other approved laboratory for analysis of **LAM or other biomarkers**.

3.7 POTENTIAL RISKS AND BENEFITS OF STUDY PROCEDURES

POTENTIAL RISKS

- (1) Risk of spontaneous sputum collection.
Sputum collection is very safe for the research participant but does pose a risk to the study staff and/or bystanders or aerosolized transmission of a respiratory pathogen. Sputum collection will be explained to the participant by a qualified research nurse who will ensure the participant has access to a well-ventilated area, preferably outdoors, that is isolated from other people. The research nurse will wear a fit-tested N95 respirator at all times.
- (2) Risk of chest x-ray.
Chest x-ray is a very safe procedure that exposes adults to a very low dose of radiation. All chest x-rays will be performed by licensed radiographers according to their safety protocols. It has been shown that even for pregnant women the benefit of dCXR for TB screening outweighs the risk of exposure of the foetus to radiation⁶³. To minimize risk of exposure, a lead shield apron will be worn around the waist of all participants.
- (3) Risks of venepuncture.
Venepuncture for blood sampling carries a minimal risk of pain, bruising bleeding and rarely infection. These reactions usually last only a short time (1-3 days). The risk of infection will be minimized by the use of sterile, single-use needles. Fainting or light-headedness may also occur, and usually lasts only a few minutes. Experienced, skilled staff will obtain blood samples.
- (4) Stress response to previously unknown HIV or TB diagnoses.
Learning of a new TB or HIV diagnosis may cause emotional distress. Results will be communicated sensitively by trained nurses or physicians, who will provide post-test counselling and assess the need for additional support. Participants experiencing severe distress or suicidal ideation will receive immediate psychological or medical referral as appropriate.

(5) Risk of breach of confidentiality.

Strict confidentiality will be maintained. All study data and records will be de-identified, coded, and stored in secure, access-controlled databases. Disclosure of results will occur only where required by local regulations (e.g., notification of TB or HIV results to health authorities) and in accordance with institutional agreements and participant consent.

POTENTIAL BENEFITS

- (1) All participants will benefit from being screening for TB. Any positive cases will be referred for treatment.
- (2) All participants who are tested for HIV will receive pre- and post-test HIV counselling and learn their HIV status. Those adolescent and adult participants who are HIV-positive will learn their HIV viral load. The results and counselling will improve their knowledge of their personal health and empower them to make positive health choices.
- (3) All participants who have results that require clinical action will be promptly referred to address abnormalities revealed. Standard of local care will be strengthened using study resources to support appropriate TB investigation, management, and implementation of TPT use in line with national guidelines
- (4) Participants may derive satisfaction from knowing that the study results could contribute to a better understanding of asymptomatic TB and its impact on the global TB epidemic.

3.8 STUDY OUTCOMES/ ANALYSES

The study is designed to assess both the transmission of Mtb within households and the diagnostic performance of current and novel tools for detecting asymptomatic TB. The outcomes are grouped into primary and additional outcomes categories as outlined below.

CORE STUDY

Primary endpoint: Cumulative prevalence of child household contact IGRA positivity or confirmed TB (TB-C) at 10 weeks after diagnosis of the index case.

Additional outcomes/ analyses:

- (1) Proportion of children that convert from negative IGRA status at baseline to a positive IGRA status at 10-week visit.
- (2) Proportion of children with a positive plasma cell free Mtb DNA assay and positive Mtb-specific T cell activation assay, stratified by household group.
- (3) Whole genome sequencing of Mtb isolates from people with TB-C and household contacts.

CASE-CONTROL PHENOTYPING STUDY (SUB-STUDY 1)

- (4) Sensitivity, specificity, positive predictive value, negative predictive value, yield, feasibility, acceptability of digital chest x-ray with computer aided diagnosis (dCXR/CAD), sputum Nucleic Acid Amplification Test (NAAT), Mycobacteria Growth Indicator Tube (MGIT), tongue swab NAAT, and bioaerosol collection facemask mask NAAT to detect aTB-C.
- (5) Symptoms, health outcomes quality of life, comorbidities, nutritional status, and TB history, relative to group and W4SS status at screening.

(6) Proportion and characteristics of participants with detectable exhaled breath condensate lipoarabinomannan (LAM), positive plasma cell free Mtb DNA assay, positive Mtb-specific T cell activation assay and additional blood-based TB biomarkers, stratified by group.

TB UNCONFIRMED (TB-U) COHORT (SUB-STUDY 2)

(7) Time to event and factors associated with microbiological or clinical progression in participants with initially untreated aTB-U.

(8) Plasma biomarkers (including cell free Mtb DNA, Mtb-specific T cells, transcriptional signatures) that correlate with progression from aTB-U in the 12 months after TB screening

(9) Proportion and characteristics of participants with TB screening results suggestive of (TB-U) who have a subsequent positive sputum GeneXpert Ultra, sputum MGIT, tongue swab NAAT or Bioaerosol collection facemask mask NAAT.

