Based on data from a health and demographic surveillance system in northern KZN, children aged 2-14 years old are 32.0% of the resident population, and 39.8% of households have at least one resident child in this age group. In the households with children in this age group, the median number of children per household is 2 (IQR 1-3) and mean is 2.58 (SD=1.63). A study done across two provinces (Limpopo and Free State) showed tuberculin skin test positivity of 17%.³⁰ The recently completed (not published) household (HH) contact tracing conducted in the Hlabisa sub-district in northern KZN found 18.4% (95% CI:15.-21.5%) IGRA positivity in child contacts of symptomatic clinic diagnosed people with TB. The IGRA positivity was 16.4% (95% CI: 7.8%-28.8%) amongst child contacts of people with aTB diagnosed at the clinic and 7% (95% CI: 3.5% to 10.5%) in community controls with no person with TB in the household.

In Bandung city, 59.0% of households have at least one child aged 2-14 years, with a mean of 1.5 (SD=0.7). In a study comparing IGRA and TST in Bandung City in 196 households with a person with TB, 299 household-exposed children aged 6 months to 9 years old and 72 age and sex matched neighbourhood-exposed children were recruited and tested. Of the household contacts, 156 (52%) tested positive using IGRA and 144 (48%) using TST³¹. Of the neighbours 15 of 72 tested (21%) were IGRA positive and 7 (21%) were TST positive. Of 38 children with a follow-up IGRA test at 3 months, 8 of 23 (35%) initially IGRA negative individuals had IGRA conversion and 3 of 15 (20%) initially IGRA positive individuals had IGRA reversion. Another study recruited 1,347 TB household contacts of 462 known TB

cases³². Of the contacts, 170 were children aged 5 to 9 years; 96 of 168 (57%) tested were IGRA positive among the children, and a further 15 amongst 67 (22%) tested after 14 weeks became IGRA positive amongst the 72 who were initially IGRA negative.

INTERFERON-GAMMA RELEASE ASSAY

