In addition to assessment of genotypic links, other approaches that are recommended for estimating Mtb infection resulting from transmission are TB notification rates, tuberculin skin tests (TST) and or Interferon-gamma release assays (IGRA)²⁴. IGRA such as the QuantiFERON Gold In-Tube (QGIT) test, detect immunoreactivity to highly specific Mtb antigens from a blood sample. The drawback of the QGIT test is that it requires laboratory processing; however, many laboratories in South Africa and other high TB prevalence setting already have sufficient expertise and experience with these tests. The QGIT test involves a simple blood draw and participants are not required to return for another 'in person' visit for interpretation. Results also do not rely on the subjectivity of TST readers, for example, and QGIT is more sensitive and specific than TST in people living with HIV (PLHIV), including those with previous BCG vaccination^{33,34}. In addition to test conversion, IGRA tests are subject to significant early test reversion in case contacts, which has not been fully explained beyond that which occurs close to the cut-off value³⁵⁻³⁷. Therefore in this study we will measure Mtb transmission and new infection from people with aTB by using the IGRA/QGIT status in child household contacts as the endpoint to quantify infectiousness and compare the rates with those with community controls.

NOVEL TB DIAGNOSTIC TOOLS

The identification of novel screening and diagnostic tools capable of detecting aTB is a research priority for WHO. Existing modalities, demonstrate limited sensitivity for paucibacillary disease and are often constrained by cost, infrastructure requirements, and operational complexity, restricting their applicability in field settings. Advances in biomarkers, molecular diagnostics, and non-sputum-based sampling strategies have yielded a pipeline of promising tools at various stages of development. However, evaluation of their feasibility and performance to detect asymptomatic disease is a critical knowledge gap that needs to be addressed in order to inform their potential role in scalable aTB detection strategies.

BIOAEROSOL SAMPLING

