2. OBJECTIVES

The **co-primary objectives** of the study are to compare Mtb infection, as defined by interferon release assay (IGRA) positivity, in child (2-14 years) household contacts of adults with bacteriologically-confirmed asymptomatic TB (aTB-C), with:

1. children in households with no adult with TB
2. children who are household contacts of adults with bacteriologically-confirmed symptomatic TB (sTB-C)

The **secondary objectives** are to:

1. Evaluate the diagnostic performance, feasibility, and acceptability of current tools for detecting aTB, including digital chest X-ray with computer-aided diagnosis (dCXR/CAD) and sputum Xpert, and sputum Mycobacteria Growth Indicator Tube (MGIT)
2. Evaluate the performance of novel diagnostic and screening tools to detect aTB including tongue swab NAAT, bioaerosol NAAT, exhaled breath condensate for lipoarabinomannan, cell free Mtb DNA and Mtb-specific T cell activation.
3. Characterize the features and longitudinal outcomes of sub-groups of people with aTB, including those with dCXR/CAD findings suggestive of TB but who are sputum Xpert & culture negative.

4. Establish a biobank and conduct studies of immune responses to understand the biology of aTB and define correlates of progression and resolution.
5. Model the contributions of aTB to global TB transmission and incidence and the potential impact of interventions to detect and treat this disease phenotype
6. Evaluate the proportion of child household contacts who convert from baseline negative to positive IGRA at 10-week visit or have a positive blood biomarker (including cell free DNA assay or positive Mtb-specific T cell activation assay).
7. Define the proportion of participants with TB screening results consistent with sTB-U who have a subsequent positive sputum Xpert, sputum MGIT, tongue swab NAAT or facemask NAAT.
8. Identification of transmission clusters using whole genome sequencing of Mtb strains obtained from participants with aTB-C, sTB-C and their household contacts.

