3.4 STUDY SCHEDULE

A summary of study visits is provided in **Table 2**, and the flowchart of Schedule of Procedures is presented in **Appendix C**.

Table 2: Schedule of study procedures for participants enrolled in the asymptomatic TB transmission in Indonesia and South Africa study

Cross-sectional study of Household Mtb	
Visit 0: Household identification and consent
 
 • Identify geospatial areas for enumeration • Informed consent by household head • Minimal Household enumeration to determine eligibility • Dwelling/House description data
--	--

infection (core study)	
Visit 1: Screening and enrolment
 
 • Consent and enrolment of all adolescents and adults HH members • Demographics • Basic Health Questionnaire • Symptom screening (including W4SS) • Minimal physical examination (weight, height) • Sputum collection for Xpert and MGIT culture • Tongue swab NAAT collection for participants unable or refuse to produce sputum[#] • Digital chest x-ray with computer aided detection (dCXR/CAD) 
Visit 2.1 and 2.2: Community or clinic IGRA measurements (weeks 0-2 and or 8-10)
 
 • Individual assent and parent/ guardian consent for child household contacts • Structured questionnaire on contact patterns with index person and detailed dwelling/House description data • Symptom screening (W4SS modified for children) • If TB symptoms, sputum collection • Weight, height, mid upper arm circumference (MUAC) • Venous blood for IGRA testing (all children at visit 2.1; at week 8-10 (visit 2.2), only repeat IGRA if visit 2.1 IGRA was negative) • Venous blood samples -for HIV^{\$}, cell-free Mtb DNA, Mtb-specific T cells and biobanking • If any symptoms or signs suggestive of TB are identified, refer to the appropriate health facility and provide support for TB investigation and treatment in accordance with national guidelines • Referral for TB preventative therapy (TPT) for all HH contacts of people with TB (visit 2.2) 
Visit 2.3: Community, clinic or telephonic review and referral (weeks 2-14), Provide IGRA status
 
 • Issue any outstanding results for adults • Follow-up on TB treatment or TPT initiation • End of study visit for cross-sectional study

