A community, or clinic-based follow-up visit or telephonic contact will be conducted between weeks 2 and 14 (**Visit 2.3**) for participants with positive results. This visit will be used to provide IGRA and sputum results (where sputum was collected) and to confirm that appropriate referral to the local health clinic for TPT initiation or TB treatment, as indicated, has occurred. The study team will provide support to strengthen local health care facilities by building capacity in the provision of TPT for household contacts of participants diagnosed with TB, in accordance with national guidelines.

In South Africa, HIV results will be provided with post-test counselling using language appropriate to the child's age and maturity. Children aged 12–14 years may receive their results without a parent or guardian present but will be encouraged to involve their parent or guardian in the discussion and ongoing support.

Participants with negative results will be contacted via telephone or SMS. This visit will mark the End-of-Study visit for household contacts.

SUB-STUDIES 1 and 2

Within two weeks of TB screening, eligible participants will be invited to attend the research clinic for **Visit 1.1**. Participants will remain blinded to their screening results at the time of the visit. At Visit 1.1,

individual consent or assent will be obtained for participation in the sub-studies. This visit will include all participants being enrolled in either Sub-study 1 (aTB-C, sTB-C, and control participants) or Sub-study 2 (TB-U participants).

At the clinic, a **blinded structured questionnaire** will be administered to collect detailed information on symptoms, quality of life, functional status, and health outcomes. This will be followed by a comprehensive physical examination, including assessment of vital signs, height, weight, lymphadenopathy, and breath sounds. Two samples, either an early-morning and spot specimen or two spot specimens, as per site procedures will be collected for Xpert and MGIT culture testing. Participants whose screening molecular test was a positive tongue swab NAAT, will have 3 sputum specimens collected.

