APPENDIX C : SCHEDULE OF STUDY PROCEDURES

Table 7: Schedule of Study Procedures

Study	Cross- Sectional study (core study)					Phenotypic (Sub-study 1)	Cohort (Sub-study 2)			
	Adolescents & Adults (> 15 yrs.)		Children (2-14 years)				Adolescents & Adults			
Visit	Visit 0	Visit 1	Visit 2.1	Visit 2.2	Visit 2.3	Visit 1.1	Visit 1.2	Visit 1.3	Visit 1.4	Visit 1.5
Time point		screening	Week 0-2*	Week 8-10	Week 2-14	Week 1-8	Month 3	Month 6	Month 9	Month 12
Household census and consent	x									
Informed consent / assent		x	x	x ^b		x				
Demographics		x								
Medical History		x				x				
Structured questionnaire			x	x ^b		x				
TB Symptom Screening (W4SS)		x	x	x						
TB Symptom Assessment (full)						x	x	x	x	x
Clinical Assessment incl. quality of life, functional status							x	x	x	x
Physical Examination -limited		x	x	x ^b						
Physical Examination - full						x	x	x	x	x
Sputum sampling – NAAT & MGIT		x	x ^a	x ^a		x	x	x	x	x
Blood sample- HIV Counselling and testing\$			x	x ^b		x				
Blood sample- IGRA			x	x ^c						
Blood sample – HbA1c, full blood count						x				
Blood sample – Mtb-specific T cell activation; Mtb cell free DNA; biobanking			x	x		x	x	x	x	x
Digital X-Ray with CAD		x					x	x	x	x
Novel tests – tongue swab NAAT; facemask; exhaled breath condensate						x	x ^d	x ^d	x ^d	x ^d
Physician review						x	x	x	x	x
Referral to DOH – TB assessment, as required			x	x	x	x	x	x	x	x
Referral to DOH – TPT, as required			x	x	x					

x^a: if child is symptomatic; **x^b:** if adult diagnosed on MGIT> 2 weeks after collection, child consent/assent, structured questionnaire and HIV will be taken at visit 2.2; **x^c=** : IGRA repeated at visit 2.2 if negative at visit 2.1 **x^d:** facemask and exhaled breath condensate to be collected at all study visits in a subset of TB-U cohort participants (first n=100); * If adolescent/ adult MGIT positive within 2 weeks the child HHC will be eligible for visit 2.1 & 2.2; if MGIT positive> 2weeks, the child HHC will only attend visit 2.2; \$: HIV testing of children will only occur in South Africa

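### IGRA conversion is a bare change from negative to positive with one-way retesting, so some conversions will be retest noise or infection already present at baseline

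*Protocol*

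**What the plan says.** Protocol section 3.8 lists as additional outcome (1) of the core study the "Proportion of children that convert from negative IGRA status at baseline to a positive IGRA status at 10-week visit". Secondary objective 6 in section 2 uses the same rule: children who "convert from baseline negative to positive IGRA at 10-week visit". Neither asks for a minimum rise in interferon-gamma, an uncertainty zone or a repeat test.

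Retesting runs in one direction. Table 2 in section 3.4 says of Visit 2.2: "only repeat IGRA if visit 2.1 IGRA was negative". Appendix C agrees: "IGRA repeated at visit 2.2 if negative at visit 2.1". Visit 2.2 is the last blood draw. Of Visit 2.3, section 3.5 says "This visit will be used to provide IGRA and sputum results", so no conversion can be confirmed within the schedule.

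The protocol knows that the test is unstable. The Background reports that in Bandung "3 of 15 (20%) initially IGRA positive individuals had IGRA reversion". It adds that early reversion in contacts is a phenomenon "which has not been fully explained beyond that which occurs close to the cut-off value". The sensitivity analyses in section 5.2 deal with infection acquired outside the household and with symptom misclassification, not with IGRA variability.

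The quantitative result will exist. Under section 3.6, blood is "incubated according to manufacturer instructions, and plasma analysed for interferon-gamma" concentration.

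**The concern.** When only negatives are retested and any later positive counts, retest noise can add conversions but the matching reversions are never seen. Two kinds of child are then counted as new infections: uninfected children with a false positive second test, and children already infected whose first test was falsely negative. The second kind matters for comparing groups, because such children are more common where baseline positivity is higher. Conversion per baseline-negative child could then look higher in aTB-C and sTB-C households than in control households with no infection acquired between the visits. Positives found at Visit 2.2 also enter the cumulative primary endpoint.

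**Working it through.** **Inputs from the protocol**
- Cited Bandung children retested at 3 months (Background): 8/23 = 34.8% conversion and 3/15 = 20.0% reversion. Both match the stated 35% and 20%. The exact 95% CI for 3/15 is 4% to 48%.
- Second Indonesian study (Background): 15/67 = 22.4% conversion at 14 weeks.
- IGRA positivity p (Tables 3 to 5): Bandung 20% control, 32% aTB-C (control plus the 12-point minimum detectable difference), 40% sTB-C; KwaZulu-Natal 7%, 14% and 18%. Using these as baseline positivity is an assumption.

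**Step 1: identity under no change.** If nothing truly changes between visits, noise conversions and noise reversions are equal in number. With r the reversion fraction, conversion per baseline-negative child = p × r / (1 − p). At p = 20%, r = 20%: 0.20 × 0.20 / 0.80 = 5.0%.

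**Step 2: does r stay the same across groups?** The result depends on this. Take a bivariate-normal test-retest model, calibrated to 20% reversion at p = 20% (correlation 0.936), with the same reliability in every group. Reversion then falls as p rises.

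| Bandung group | p | r, common reliability | conversion per negative | conversion if r = 20% in every group |
|---|---|---|---|---|
| Control | 20% | 20.0% | 5.0% | 5.0% |
| aTB-C | 32% | 16.0% | 7.5% | 9.4% |
| sTB-C | 40% | 13.9% | 9.2% | 13.3% |

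The aTB-C to control ratio is 7.5/5.0 = 1.5 with common reliability and 9.4/5.0 = 1.9 with r fixed at 20%. With r fixed, KwaZulu-Natal gives 1.5%, 3.3% and 4.4%. With r = 10% in every group, the Bandung figures halve to 2.5%, 4.7% and 6.7%.

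**Step 3: where does the gradient come from?** Take two independent tests with sensitivity s and specificity c (both assumed). True prevalence is π = (p − (1 − c)) / (s − (1 − c)). Conversion per negative = [π s(1 − s) + (1 − π) c(1 − c)] / (1 − p). Bandung, control / aTB-C / sTB-C:
- s = 1, c = 0.97 (false positives only): 3.0% / 3.0% / 3.0% per negative. Over all children it is 2.4% / 2.0% / 1.8%, so the order reverses.
- s = 0.95, c = 0.97: 4.1% / 5.1% / 6.1% per negative.
- s = 0.80, c = 0.97: 7.3% / 11.5% / 15.3% per negative.

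The gradient per negative child therefore needs some infected children to be missed at baseline.

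**Step 4: primary endpoint.** The addition to cumulative positivity is p × r. With common reliability, Bandung control goes from 20% to 24.0% and aTB-C from 32% to 37.1%, so the risk difference moves from 12 to 13.1 points. With r = 20% in every group it moves to 38.4 − 24.0 = 14.4 points, while the aTB-C to sTB-C ratio stays at 38.4/48.0 = 0.80.

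**Step 5: effect of a minimum rise.** In the common-reliability model, also require a rise of at least 1.96 × √2 × the within-child SD. The Bandung no-change rates fall from 5.0% / 7.5% / 9.2% to about 0.7% / 1.1% / 1.3%. The aTB-C minus control difference falls from 2.5 to about 0.4 points, but the ratio remains about 1.5.

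**The case against.** The strongest reply is that section 3.8 is a short outcome list. No cut-off is stated, concentrations are measured, and a quantitative rule may sit in an SAP or laboratory procedure that is not shown. That limits the weight of the point. It does not remove it, because the protocol states a status-only rule in both places and fixes the one-way retest schedule.

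The cited data also do not fit a noise-only account. Under no change, 3 reversions would come with about 3 conversions (3/23 = 13%), but 8 were seen. Real conversion is plausible, and noise would explain only a part. The 3/15 figure is imprecise and comes from Bandung alone.

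A reader might infer more than the documents support:
- *That TB households must show more noise conversions than controls.* Step 3 shows equal rates per negative under pure false-positive noise, and a reversal over all children. As counts, the 2:1 control ratio gives controls more than aTB-C households in every scenario run (for example 26 against 18 in Bandung at s = 0.80, c = 0.97).
- *That the excess is 1.9-fold.* This needs reversion to be 20% in every group, hence a less reliable test where positivity is higher.
- *That the primary endpoint is simply inflated.* Counting infected children missed at baseline is better ascertainment for a cumulative prevalence, and with equal r the aTB-C to sTB-C ratio does not change.
- *That a between-group test of conversion is planned.* Outcome (2) is stratified by household group; outcome (1) is not stated to be. Section 5.1 names IGRA positivity, not conversion, as the transmission proxy.

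**Conclusion.** The point holds in a limited form. As written, additional outcome (1) and secondary objective 6 will count some retest noise and some infection already present at baseline as new conversion, and nothing in the schedule or the stated sensitivity analyses would reveal it. Per baseline-negative child, the spurious rate rises with baseline positivity if baseline sensitivity is below 100%.

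For Bandung, about 5.0%, 7.5% and 9.2% (control, aTB-C, sTB-C) is illustrative. It assumes that all reversion is noise, 20% reversion at 20% positivity, common reliability, and planned positivity equal to baseline positivity. Given the interval of 4% to 48% around 3/15, the true figures could be much smaller or larger. This concerns an additional outcome and a secondary objective. The effect on the primary endpoint is uncertain and partly legitimate, so it calls for a sensitivity analysis and not for a changed endpoint.

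**What to change.** For additional outcome (1) and secondary objective 6, pre-specify before between-group data are seen a conversion definition that requires crossing the cut-off plus a minimum rise in interferon-gamma exceeding visit-to-visit variability. State the cut-off and use children with a negative baseline IGRA as denominator. Report this alongside simple crossing.

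Add one sensitivity analysis of the primary endpoint that does not count Visit 2.2 positives failing the minimum rise. Limit it to children tested at both visits, since those recruited after a late MGIT result have only Visit 2.2 and no baseline value from which to measure a rise.

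The cost is wording and one extra analysis, with no extra blood or visits. Some true converters with small rises will not be counted under the stricter definition. The change reduces absolute noise and the spurious risk difference but leaves the relative gradient between groups, so a ratio of conversion rates still needs cautious reading.
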